2.2 Safety evaluation index

2.2.1 Key safety indicators

• Proportion of CTCAE grade 3 toxicity

Proportion of subjects with grade 3 toxicity in the trial cycle.

Calculation formula: Proportion of CTCAE grade 3 toxicity = number of subjects with CTCAE grade

3 toxicity in the test cycle / total number of subjects ×100%;

• Proportion of CTCAE grade 4 and 5 toxicity

Proportion of participants with grade 4 and 5 toxicity during the trial cycle.

Calculation formula: Proportion of CTCAE grade 4 and 5 toxicity = number of subjects with CTCAE

grade 4 and 5 reactions in the trial cycle / total number of subjects \times 100%;

2.2.2 Secondary safety metrics

Confidential Information Page 6 / 17

Date: 2022-11-11

Proportion of CTCAE grade 1 and grade 2 toxicity

Proportion of participants with Grade 1 and Grade 2 toxicity in the trial cycle.

Calculation formula: Proportion of CTCAE grade 1 and grade 2 toxicities = number of subjects with

CTCAE grade 1 and 2 toxicity in the trial cycle/total number of subjects $\times 100\%$;

• Laboratory tests (blood routine, coagulation routine, urine routine, liver function, renal function)

Laboratory tests were performed and, in the judgment of the investigator, clinically significant changes

in laboratory markers (before and after radiation therapy was administered) were reported.

ECOG Grade of Strength Status

ECOG performance status grading assessment was performed and clinically significant changes in

examination results (before and after radiotherapy) were reported at the discretion of the investigator.

• Tumor recurrence rate

The ratio of the number of subjects with tumor recurrence to the total number of subjects. Tumor

recurrence refers to the growth of a tumour that is clinically controlled after radiotherapy and grows over a

period of time, and is of the same nature as the primary tumor. Recurrence referred to clinically mostly

refers to local recurrence, such as recurrence of residual organs, irradiation fields, and adjacent organs

affected. Prostate cancer recurrence refers to biochemical recurrence, and PET-CT is required to confirm

that the tumor has metastasized to lymph nodes or distant metastases.

Calculation formula: tumor recurrence rate = number of subjects with tumor recurrence / number of

total subjects $\times 100\%$;

Incidence of adverse events

An adverse event (AE) is an unfavorable medical event that occurs during the course of a clinical trial,

whether or not device related.

Calculation formula: incidence of adverse events = number of subjects with adverse events in this group

/ number of all subjects in this group $\times 100\%$;

• Incidence of serious adverse events

A Serious Adverse Event (SAE) is a serious adverse event that occurs during a clinical trial that results

in death or serious deterioration of health, including fatal illness or injury, permanent defects in body

structure or function, hospitalization or prolonged hospital stay, medical or surgical intervention to avoid

permanent defects in body structure or function, fetal distress, Fetal death or congenital anomalies,

congenital defects and other events.

Confidential Information Page 7 / 17

Statistical Analysis Plan Version: V1.0
Date: 2022-11-11

Calculation formula: incidence of serious adverse events = number of subjects with serious adverse

events in this group / number of all subjects in this group $\times 100\%$;

• Incidence of device defects

Device defects refer to the unreasonable risk that medical devices may endanger human health and life

safety under normal use during clinical trials, such as crashes.

Calculation formula: incidence of device defects = number of device defects / number of device use

 $\times 100\%;$

3 Statistical analysis set

The following analysis sets were defined in this trial for statistical analysis.

Full Analysis Set (FAS): According to the basic principles of intention-to-treat analysis, all participants who

received at least one treatment with an investigational device and at least one post-baseline observational data

will be included in the FAS. FAS will be used as the main population for the baseline data and effectiveness

evaluation sensitivity analysis of this study. Exclusion is only possible in very limited circumstances, including

cases where important enrollment criteria have been violated and no observational data have been available after

enrollment.

Per-Protocol Set (PPS): is a subset of FAS and refers to subjects with measurable lesions at baseline who

have completed at least one primary efficacy measure assessment after baseline. PPS will be the main population

in the evaluation of the effectiveness of this study.

Safety Set (SS): All participants who received at least one treatment with an investigational device and had

at least one safety evaluation. SS will be the primary population for safety analysis in this study.

The baseline characteristics will be assessed using the full analysis set, the effectiveness will be assessed

using both the full analysis set and the conformance set, and the safety analysis will use the safety dataset.

4 data processing

4.1 Processing of data from unscheduled visits

The processing of unscheduled event data is agreed as follows:

In addition to the scheduled visit data, unscheduled event data should also be considered when judging the

baseline value. Unless otherwise specified, the last non-missing test value before the first treatment is used as the

baseline value.

Safety trial (e.g., laboratory tests, vital signs) metrics aggregated by visit, and only scheduled visit test results

are summarized.

Confidential Information Page 8 / 17

rsion: V1.0 Date: 2022-11-11

When performing the worst observational data carry-over and fill (WOCF) analysis for the main effectiveness evaluation indicators, the unplanned event data will be considered in addition to the planned visit data, but only the planned visit data will be descriptively summarized.

All unscheduled event data should be tabulated.

Unless otherwise specified, the data of unscheduled visits will be summarized and tabulated according to the above principles, otherwise they will be described in a footnote under the statistical analysis table.

4.2 Handling of missing dates for various events

For various events (previous/concomitant medications, concomitant treatments, AEs, etc.), according to the definition and nature of different events, the fill-in rules for the absence of their start/end dates are agreed. If the end date of each event is missing, it will not be filled, and the rules for missing the start date are shown in Table 2.

Table 2 Incomplete filling rules with start dates

Missing	Fill the rules
values	
day	If the year and month are the same as the year and month of the treatment start date,
	and the end date is after the treatment start date or is missing, the treatment start
	date is used to fill in;
	Otherwise fill for 1 day.
Day/Month	If the year is the same as the treatment start date, and the end date is after the
	treatment start date or is missing, the treatment start date is used to fill in;
	Otherwise fill for January 1.
Day/Month/	If the end date is after the treatment start date or is missing, the treatment start date
Year	is used to fill in;
	Otherwise, no filling will be carried out.

4.3 Effectiveness indicators are missing

When analysing the main effectiveness evaluation indicators based on PPS, it is not necessary to consider filling them.

In the sensitivity analysis of the main effectiveness evaluation indicators based on FAS, the missing values of the main effectiveness evaluation indicators were not filled.

The missing values of qualitative secondary effectiveness evaluation indicators ORR and DCR were filled by the method of worst observational data carryover (WOCF).

The missing value of the quantitative secondary effectiveness evaluation index DOR was not filled.

Other secondary effectiveness evaluation indicators, such as tumor markers, tumor-specific symptoms, and

Confidential Information Page 9 / 17

rsion: V1.0 Date: 2022-11-11

product ease of use, were not filled.

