Definition of indicators: CR or PR after the end of treatment is considered objective remission, prostate cancer has no biochemical recurrence at the end of the last treatment, and no regional lymph nodes or distant metastasis are considered objective remission. Proportion of participants who experienced objective remission at each time point after the end of the last treatment.

Metric type: Qualitative.

Data collection time: screening period, 1 month \pm 7 days, 3 months, \pm 7 days after the end of the last treatment.

Evaluation time: 1 month \pm 7 days, 3 months, \pm 7 days after the last treatment.

Site of evaluation: Tumor receiving radiation therapy.

Evaluation method: The changes in tumor CT or MRI imaging before and after treatment were evaluated by an independent imaging review panel according to RECIST 1.1. At 3 months of radiographic evaluation, if PD is found, PET-CT is required to confirm it.

Calculation formula: ORR = number of subjects in objective response / total number of subjects × 100%.

Criteria: See RECIST 1.1 for details. At the time of 3-month imaging evaluation, if the patient is found to have PD, PET-CT examination is required to confirm it, if progress is confirmed, it is recorded as PD, if progress cannot be confirmed, it may be false progression, and it is recorded as SD. If prostate cancer does not have biochemical recurrence, PET-CT examination is not required, and there is no metastasis by default, which is regarded as objective remission, and if biochemical recurrence occurs, it is regarded as not objectively remission, and PET-CT is required to confirm tumor metastasis.

Note: Participants who aborted the trial for any reason (other than loss to follow-up) before the end of the last radiotherapy were considered to have not responded objectively. Disease site evaluation uses the same approach as baseline, including consistent contrasted/non-contrast scans and prompt scanning. If changes are needed, the case must be discussed with a radiologist to determine whether an alternative approach is possible. If not, the objective situation in the future is unclear.

(2) Time to sustained remission (DOR).

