Definition of indicators: the occurrence of CR, PR and SD after the end of treatment is disease control; No biochemical recurrence at the end of prostate cancer treatment, no regional lymph nodes or distant metastases, considered disease control. Proportion of participants who developed disease control at one month after the end of the last treatment.

Metric type: Qualitative.

Data collection time: screening period, 1 month \pm 7 days after the end of the last treatment.

Evaluation time: 1 month \pm 7 days after the last treatment.

Site of evaluation: Tumor receiving radiation therapy.

Evaluation method: The changes in tumor CT or MRI imaging before and after treatment were evaluated by an independent imaging review panel according to RECIST 1.1. At 3 months of radiographic evaluation, if PD is found, PET-CT is required to confirm it.

Calculation formula: DCR = number of disease control subjects / total number of subjects \times 100%.

Criteria: See RECIST 1.1 for details. At the time of 3-month imaging evaluation, if the patient is found to have PD, PET-CT examination is required to confirm it, if progress is confirmed, it is recorded as PD, if progress cannot be confirmed, it may be false progression, and it is recorded as SD. If prostate cancer does not have biochemical recurrence, PET-CT examination is not required, and there is no metastasis by default, which is regarded as tumor control, and if biochemical recurrence occurs, it is regarded as tumor not controlled, and PET-CT is required to confirm tumor metastasis.

Note: Participants who aborted the trial for any reason (other than loss to follow-up) before the end of the last radiotherapy were considered to have PD or was uncontrolled. Disease site evaluation uses the same approach as baseline, including consistent contrasted/non-contrast scans and prompt scanning. If changes are needed, the case must be discussed with a radiologist to determine whether an alternative approach is possible. If not, the objective situation in the future is unclear.

(4) Tumor markers (if needed)

Reason for selection: The Guidelines for the Review of Clinical Evaluation Technologies of Proton Carbon Ion Therapy System (CFDA Circular No. 4, 2018) suggests that changes in tumor markers and functional imaging parameters should be used as reference factors for effectiveness evaluation.

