- (3) The missing values of DCR and primary safety evaluation indicators
 (proportion of CTCAE grade 3 toxicities, proportion of CTCAE grade
 4 and 5 toxicities) at 3 months after the end of treatment can be estimated using worst-case scenarios.
- (4) The missing values of qualitative secondary effectiveness evaluation indicators ORR, DCR and long-term follow-up effectiveness evaluation indicators can be estimated using worst-case scenarios;
- (5) The missing values of quantitative secondary efficacy evaluation indicators DOR, tumor markers, product ease assessment and long-term follow-up effectiveness evaluation indicators were not estimated.
- (6) Erroneous, unreasonable data (out-of-range data and data that contradicts other data or indicators of the study protocol) can be treated as missing values;
- (7) Worst-case estimates are used for missing values for all minor safety indicators;

- (8) The sensitivity analysis of the main effectiveness evaluation indicators and main safety evaluation indicators after treatment was carried out in the whole analysis center.
- (9) The sensitivity analysis of all secondary effectiveness evaluation indicators after treatment was carried out in the whole analysis center.
- (10) For all secondary safety evaluation indicators after treatment, sensitivity analysis was carried out in the security dataset.

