ECOG	Eastern Cooperative Oncology Group	Eastern Oncology Collaborative Group
FAS	Full Analysis Set	Full analysis set
ICH	The International Council for Harmonisation of Technical Requirement for Pharmaceuticals for Human Use	International Harmonization Council for Technical Requirements for Pharmaceuticals for Human Use
MedDRA	Medical Dictionary for Regulatory Activities	Medical Dictionary of Regulatory Activities
NYHA	New York Heart Association	New York Heart Society
OIS	Oncology Information System	Oncology Information System
ORR	Objective Response Rate	Objective response rate
PD	Progressive Disease	Disease progression
PET	Positron Emission Tomography	Positron emission tomography
PN	Preferred Name	Preferred name
PPS	Per-Protocol Set	Conforms to the scenario set
PR	Partial Response	Partial relief
PSA	Prostate Specific Antigen	Prostate-specific antigens
PT	Preferred Terms	Preferred term
SAE	Serious Adverse Events	Serious adverse events
SAP	Statistical Analysis Plan	Statistical analysis plan
SAS	Statistical Analysis System	Statistical analysis system
SD	Stable Disease	Stable disease
SLD	Sum of Longest Diameter	Sum of longest diameters of tumors
SOC	System Organ Class	Systematic organ classification
SS	Safety Set	Security datasets
TEAE	Treatment Emergent Adverse Event	Adverse events during the treatment period
TNM	Tumor, Node, Metastasis	Tumors, lymph nodes, metastases
WHODD	World Health Organization Drug Dictionary	World Health Organization Dictionary of Medicines

Page 1 / 17 Confidential Information

WOCF Worst Observation Carried Forward Worst observed data carryover

Confidential Information Page 2 / 17

Statistical Analysis Plan Version: V1.0

Date: 2022-11-11

This statistical analysis plan (SAP) refers to the E9 guiding principles of the International Council for

Harmonization of Technical Requirements for Pharmaceuticals for Human Use (ICH) Guidance for Industry:

Statistical Principles for Clinical Trials ICH E3 Guidance for Industry: Structure and Content of Clinical Study

Reports Relevant national regulations and guidelines, according to the clinical study protocol titled "Varian

ProBeam Proton Therapy System China Clinical Trial (Hefei)" (version number: V1.4, Version Date: 2022-06-

10) developed.

This SAP describes the rules for the presentation and analysis of short-term follow-up efficacy data and

safety evaluation data specified in the protocol, and describes in detail the data, variables and statistical methods

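### SAP 4.3 fills missing ORR and month-1 DCR by WOCF, which is not equivalent to the protocol's worst case and has no defined value at month 1

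*SAP*

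**What the plan says.** For the qualitative secondary indicators, Protocol 4.7.2(4) states: "The missing values of qualitative secondary effectiveness evaluation indicators ORR, DCR and long-term follow-up effectiveness evaluation indicators can be estimated using worst-case scenarios". It does not define worst case.

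For the same two endpoints, SAP 4.3 states: "The missing values of qualitative secondary effectiveness evaluation indicators ORR and DCR were filled by the method of worst observational data carryover (WOCF"). The SAP's abbreviation list expands the term: "WOCF Worst Observation Carried Forward Worst observed data carryover".

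Five other provisions bear on how the rule works:

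- **Imaging times.** Protocol 3.1.4.2 schedules ORR imaging at screening, month 1 and month 3. The secondary DCR is a month-1 measure: "Proportion of participants who developed disease control at one month after the end of the last treatment".
- **Unscheduled data.** SAP 4.1 brings these into WOCF for the primary endpoint only: "When performing the worst observational data carry-over and fill (WOCF) analysis for the main effectiveness evaluation indicators, the unplanned event data will be considered".
- **Early discontinuation.** Under the ORR note in Protocol 3.1.4.2, subjects who stop for any reason except loss to follow-up "before the end of the last radiotherapy were considered to have not responded objectively". The matching DCR note counts them as progressed or uncontrolled.
- **Denominator.** The ORR and DCR formulas in SAP 2.1.2 divide by all subjects.
- **Declared changes.** SAP section 6 mentions the protocol's worst-case rule for safety only, and adds conventions for missing AE severity and device relationship. It says nothing on ORR or DCR.

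**The concern.** A worst case assigns the unfavourable outcome to a missing assessment. WOCF assigns the worst outcome the subject has already shown. That outcome may be favourable, or there may be none to carry. With only two scheduled post-treatment response assessments, both situations can arise.

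At month 3, a subject who had responded at month 1 and was then lost keeps the response. At month 1, nothing scheduled precedes the missing value, and the SAP does not say what follows. The programmer would have to choose between keeping the subject as not controlled, dropping the subject, and carrying baseline. For DCR these choices give different rates.

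At stake are the reported ORR and month-1 DCR with their Clopper-Pearson intervals, and whether a reader can tell which missing-data rule produced them.

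**Working it through.** **Plan's own figure.** The documents give no figure for this imputation. The nearest is the sample size in Protocol 4.2.1: 42 evaluable, raised to 47 for about 10% dropout. It reproduces. With target 80%, expected value 95%, two-sided 0.05 and 80% power, the one-sample z formula with null variance under H0 gives 41.59, so 42; and 42/0.9 = 46.7, so 47. This does not bear on the imputation rule. It supplies only an illustrative number missing: 47 − 42 = 5.

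**Assumed counts.** FAS of 47, with 5 missing and 42 observed at the visit in question. Month-3 ORR: 21 of 42 observed subjects respond. Month-1 DCR: 40 of 42 are controlled (0.95 × 42 = 39.9). Intervals are 95% Clopper-Pearson.

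**Month-3 ORR.** Let k of the 5 missing subjects have been in CR or PR at month 1, and let the others have had a non-response recorded then.

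- Worst case: 21/47 = 44.7% (30.2 to 59.9), whatever k is.
- WOCF: (21 + k)/47.
- Difference: k/47, about 2.1 points per subject. It does not depend on the assumed 21.

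| k | WOCF rate | Excess over worst case |
|---|---|---|
| 0 | 44.7% (30.2 to 59.9) | 0 |
| 1 | 46.8% (32.1 to 61.9) | 2.1 points |
| 3 | 51.1% (36.1 to 65.9) | 6.4 points |
| 5 | 55.3% (40.1 to 69.8) | 10.6 points |

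**Month-1 DCR.** There is no earlier scheduled post-treatment response, so the result depends on a choice the SAP leaves open.

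| Handling of the 5 | Rate |
|---|---|
| Kept in the denominator, not counted as controlled (equals worst case) | 40/47 = 85.1% (71.7 to 93.8) |
| Dropped | 40/42 = 95.2% (83.8 to 99.4) |
| Baseline carried as no change, i.e. SD | 45/47 = 95.7% (85.5 to 99.5) |

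**Month-1 ORR.** Assume again 21 of 42 observed responders. Keeping the 5 as non-responders gives 21/47 = 44.7%; dropping them gives 21/42 = 50.0% (34.2 to 65.8). Carrying baseline as no response also gives 44.7%. So carrying baseline is conservative for ORR and favourable for DCR.

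**The case against.** The strongest defence is that no conflict exists. The protocol's wording is permissive and leaves worst case undefined, and Protocol 4.1 refers detailed methods to the SAP. SAP 4.4 also fills safety values by WOCF, and section 6 does not list that as a departure from the protocol's worst case. The authors may therefore have regarded WOCF as their way of applying it. This stands against calling the SAP a proven contradiction. It does not make the two rules equal, and it does not supply a value at month 1.

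A reader might infer that subjects with nothing to carry leave the denominator. The documents do not say so. Applied literally, the formula over all subjects gives 40/47, the worst-case result. A reader might also infer that both rates are biased upward. That is too broad: WOCF agrees with worst case at month 3 when month 1 showed no response, and the month-1 direction depends on the undefined handling.

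Five missing FAS subjects is generous. Protocol 4.4 counts as dropouts some subjects who would be outside the FAS, such as those never treated, and others who may have complete scans. The discontinuation notes already remove another part of the problem. For month 3, the PPS requires a post-baseline assessment of the primary measure, so subjects without a month-3 scan would largely be outside it. The month-3 effect therefore belongs mainly to the FAS. All of this limits the size but does not remove the gap.

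**Conclusion.** The point holds as a minor one. WOCF and worst case are different rules for these endpoints, and SAP section 6 does not note the difference. WOCF can retain a lost subject as a month-3 responder, and it gives no defined value for missing month-1 ORR or DCR.

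With an assumed 5 of 47 missing, month-3 ORR is 0 to 10.6 points above the worst case. The upper end requires all five to have been in CR or PR at month 1. It also assumes that baseline does not count as an observed response; if baseline counted as no response, WOCF and worst case would agree for ORR. Month-1 DCR ranges from 85.1% to 95.7% in the example, depending on an unstated choice.

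Only loss to follow-up and missed or unreadable scans are affected. A reader might infer that trial success is at risk. It is not: the criteria in Protocol 4.5 use month-3 DCR and grade 3 to 5 toxicity, and this rule governs neither.

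**What to change.** In SAP 4.3, replace WOCF for these endpoints with an explicit rule for the FAS analysis. A missing month-1 or month-3 ORR assessment counts as non-response, and a missing month-1 DCR assessment counts as not controlled. All FAS subjects stay in the denominator, and the observed-case rate is shown beside the result. This fits Protocol 4.7.2(4).

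If the sponsor prefers WOCF, the SAP should say whether baseline and unscheduled scans are eligible, state what happens when nothing can be carried, and list the rule in section 6.

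The cost is a sentence or two in the SAP and slightly less favourable secondary rates. No extra data are needed.
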